9.5 HIV Infection

A participant mother who has a positive test for HIV must have study product held but will not be withdrawn from the study. If the participant is subsequently determined to be HIV-uninfected according to the algorithm in [Appendix IV](#), study product may be resumed. If HIV infection is confirmed, study product will be permanently discontinued by the IoR/designee (See [Section 7.5.1](#)). Participants identified as infected with HIV and their infants, if also infected with HIV, are managed or referred for management according to the standard of care of test and treat guidelines.

The care provided at the referral sites should be at a level that meets or exceeds the community standard for HIV care and will include testing and prophylaxis for infants exposed to HIV infection through breastfeeding. Written SOPs for referral for HIV care and treatment will be in place at each study site at study start and site investigators will be encouraged to identify facilities offering psychological and social services and medical care, including ART, to people infected with HIV-1 in the study countries. Some of the research sites are part of health care institutions that provide HIV care and support and can refer breastfeeding mothers and their infants to those services. Other sites have established referral agreements with programs to expand access to ART.

At every study visit, study staff will actively follow-up on prior referrals to HIV care and support services, to determine whether the participant sought the care to which she was referred, the outcome of the referral, and whether additional referrals are needed. All follow-up actions, outcomes, counseling, and plans for next steps are documented in participant study records.

Results of study laboratory testing may be helpful in clinical management, and these results are provided to the participant and her medical provider (with her permission) as soon as they are available.

9.6 Criteria for Early Termination of Study Participation

Participants may voluntarily withdraw from the study for any reason at any time. The IoR also may withdraw participant from the study to protect her/her infant's safety and/or if she is unwilling or unable to comply with required study procedures. The PSRT must be notified of all terminations conducted per IoR discretion. Participants also may be withdrawn if NIAID, IPM, Gilead Sciences, Inc., US, local, and international government or regulatory authorities including the FDA and Office for Human Research Protections (OHRP), or site IRBs/ECs terminate the study prior to its planned end date. Every reasonable effort will be made to complete a final evaluation of participants who withdraw or are withdrawn from the study prior to completing follow-up. Study staff members will record the reason(s) for all withdrawals in participants' study records. If participants who voluntarily withdraw from the study wish to re-join the study, they may resume product use (if applicable) and follow-up through their originally scheduled study exit date, pending consultation with the PSRT.

10 ANALYTICAL CONSIDERATIONS

10.1 Overview and Summary of Design

The MTN-043 study is a Phase 3b, randomized, open-label, multi-site, mother-infant pair study, with 12 weeks of planned exposure to the DPV VR (25 mg) or oral Truvada tablet (200 mg FTC/300 mg TDF). Two hundred mother-infant pairs will be randomized to the above study products in a 3:1 ratio (VR: tablet). Mothers randomized to the DPV VR will use VR to be replaced each month for approximately 12 weeks. Mothers using Truvada tablet will take one tablet orally daily for approximately 12 weeks.

10.2 Study Endpoints

10.2.1 Primary Endpoints

Maternal safety (composite)

- All SAEs including maternal deaths in both study arms
- All Grade 3 or higher AEs as defined by the *Division of AIDS (DAIDS) Table for Grading the Severity of Adult and pediatric Adverse Events, Correct Version 2.1, July 2017 and/or Addendum 1 (Female Genital Grading Table for Use in Microbicide Studies [Dated November 2007])* in both study arms

Infant safety (composite)

- All SAEs including infant deaths in both study arms
- All Grade 3 or higher AEs as defined by the *Division of AIDS (DAIDS) Table for Grading the Severity of Adult and Pediatric Adverse Events, Corrected Version 2.1, July 2017* in both study arms

Drug detection

- Maternal plasma DPV concentrations
- Maternal blood FTC-TP and TFV-DP concentrations
- Maternal breast milk DPV concentrations
- Maternal breast milk FTC and TFV concentrations
- Infant plasma DPV concentrations
- Infant blood FTC-TP and TFV-DP concentrations

10.2.2 Secondary Endpoints

Adherence

- Participant report of frequency of study product use (e.g., missed doses for oral Truvada and VR removal/expulsions [voluntary and involuntary] and duration without VR in vagina)
- Residual drug levels in returned VRs
- Maternal plasma DPV concentrations
- Maternal blood FTC-TP and TFV-DP concentrations

Acceptability

- Self-reported attitudes about study product attributes and willingness to use their assigned study product during breastfeeding in the future
- Proportion of participants who find the study product to be at least as acceptable as other HIV prevention methods

10.2.3 Exploratory Endpoints

Expanded Acceptability

- Self-reported experiences with study products and preferences for product attributes
- Self-reported attitudes about study products and perceived attitudes of key influencers (e.g., male partners, family members, providers)

Genital Microenvironment

- Genital microflora characteristics in Gram stain and quantitative PCR
- Biomarker expression in vaginal secretions

Breastfeeding

- Duration of breastfeeding and reasons for weaning (if weaning occurs during participation)
- Timing and type of infant supplementation

10.3 Primary Study Hypotheses

It is hypothesized that:

- Maternal exposure to study products will be safe for mothers and their breastfeeding infants.
- DPV will be detectable at low levels in breast milk of participant mothers using the VR.
- FTC and TFV will be detectable at low levels in breast milk of participant mothers taking Truvada.

- DPV will be detectable in the blood of some breastfeeding infants.
- FTC-TP and/or TFV-DP will be detectable in the blood of some breastfeeding infants.

10.4 Sample Size and Power Calculations

The proposed sample size is 200 mother-infant pairs randomized 3:1 to vaginal ring vs oral Truvada.

10.5 Primary Endpoints

Maternal safety and Infant safety

To characterize the statistical properties of this study, Table 19 below presents the probability of observing zero, at least one, ten or more and fifty or more safety endpoints in each arm for various “true” event rates, ranging from low to high:

Table 19: Probability (%) of observing an event given different “true” event rates by cohort size

“True” event rate	P (0 events)		P ≥ 1 event		P (≥ 10 events)		P (≥ 50 events)	
	n=150	n=50	n=150	n=50	n=150	n=50	n=150	n=50
1%	22.15	60.50	77.85	39.50	8.94	0.00	0.00	0.00
5%	0.05	7.69	99.95	92.31	72.06	0.00	0.00	0.00
10%	0.00	0.52	100.00	99.48	96.62	0.94	0.00	0.00
15%	0.00	0.03	100.00	99.97	99.71	11.99	0.00	0.00
25%	0.00	0.00	100.00	100.00	99.99	73.78	0.85	0.00

^a Sample sizes in the table based on the proposed cohort sizes and study design. With 3:1 randomization, there will be 150 participants in the VR arm and 50 participants in the FTC-TDF arm.

An alternative way of describing the statistical properties of the study design is in terms of the 95% confidence interval for the “true” rate based on the observed data. Table 20 below shows the exact 2-sided 95% confidence intervals for the probability of an event based on a particular observed rate. For example, if none of the 150 participants receiving the VR regimen experience a safety event, the 95% exact 2-sided upper confidence bound for the true rate of such events in a particular arm of the study is 2.43%.

Table 20: Confidence intervals for endpoint rate (proportion of participants with endpoint) given number of endpoints (rows) in with number of participants (columns)

Number of events	Number of Participants	
	n=50	n=150
0	0.00, 7.11	0.00, 2.43
1	0.05, 10.65	0.02, 3.66
2	0.49, 13.71	0.16, 4.73
3	1.25, 16.55	0.41, 5.73
4	2.22, 19.23	0.73, 6.69
5	3.33, 21.81	1.09, 7.61
6	4.53, 24.31	1.48, 8.5
8	7.17, 29.11	2.33, 10.24
10	10.03, 33.72	3.24, 11.92
12	13.06, 38.17	4.2, 13.56
15	17.86, 44.61	5.71, 15.96
20	26.41, 54.82	8.34, 19.84
30	45.18, 73.59	13.92, 27.3

^a Sample sizes in the table based on the proposed cohort sizes and study design.

Maternal safety (composite)

- All SAEs including maternal deaths in both study arms
- All Grade 3 or higher AEs as defined by the *Division of AIDS (DAIDS) Table for Grading the Severity of Adult and pediatric Adverse Events, Correct Version 2.1, July 2017 and/or Addendum 1 (Female Genital Grading Table for Use in Microbicide Studies [Dated November 2007])* in both study arms

Infant safety (composite)

- All SAEs including the infant deaths and in both study arms
- All Grade 3 or higher AEs as defined by the *Division of AIDS (DAIDS) Table for Grading the Severity of Adult and Pediatric Adverse Events, Corrected Version 2.1, July 2017* in both study arms

Drug detection

The tables above can also inform the hypotheses around drug detection where number of events is the number of participants with detectable drug levels.

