2.5 Sample Size and Power

The target sample size was 200 mother-infant pairs randomized 3:1 to vaginal ring vs oral Truvada. A total of 197 mother-infant pairs were enrolled. The sample size is based upon feasibility, anticipated low drug concentrations, and the likelihood of a favorable safety profile. The statistical properties of the study are described using the probability of observed safety events defined in the primary endpoint. The probabilities of observing a safety event for various “true” event rates were calculated. For example, if the true safety event rate was 5%, the probability of observing zero safety events is 0.05% for the cohort size of 150 participants (DPV VR) and is 7.69% for cohort size of 50 participants (Truvada). An alternative way of describing the statistical properties is in terms of 95% confidence interval. For example, if none of the participants experience a safety event, the 95% exact 2-sided upper confidence bound for the true event rate is 2.43% for participant receiving the VR regimen and is 7.11% for participants receiving Truvada. The properties above also inform the hypotheses around drug detection where number of events is the number of participants with detectable drug levels. Further details of the statistical properties for this study are described in section 10.5 of the protocol.

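### Protocol Table 19 misstates the chance of seeing ten or more safety events, by up to 50 percentage points in the ring arm

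*Protocol*

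**What the plan says.** Protocol section 10.4 gives the size and allocation and no power target: "The proposed sample size is 200 mother-infant pairs randomized 3:1 to vaginal ring vs oral Truvada". Section 10.5 then describes what that size can show. It says that "Table 19 below presents the probability of observing zero, at least one, ten or more and fifty or more safety endpoints in each arm", for true event rates of 1%, 5%, 10%, 15% and 25%. The table footnote fixes the denominators: "With 3:1 randomization, there will be 150 participants in the VR arm and 50 participants in the FTC-TDF arm".

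Each row lists P(0), P(≥1), P(≥10) and P(≥50), with n=150 before n=50 in each pair. The first three rows read "1% 22.15 60.50 77.85 39.50 8.94 0.00 0.00 0.00", "5% 0.05 7.69 99.95 92.31 72.06 0.00 0.00 0.00" and "10% 0.00 0.52 100.00 99.48 96.62 0.94 0.00 0.00".

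Section 10.5 also offers the tables for another primary endpoint: "The tables above can also inform the hypotheses around drug detection where number of events is the number of participants with detectable drug levels". SAP section 2.5 repeats a few zero-event figures and then sends the reader back: "Further details of the statistical properties for this study are described in section 10.5 of the protocol".

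**The concern.** The ring-arm column for ten or more events fails a check by eye. At a 1% rate, 150 participants yield 1.5 expected events, yet the table gives almost a 9% chance of ten or more. At 5% the expected count is 7.5, yet the table gives a 72% chance of reaching ten.

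With no power calculation, Tables 19 and 20 are the only quantitative account of what this design can detect on its primary safety endpoints. A reader who trusts the 5% row would think that fewer than ten ring-arm events has a chance of 100 − 72.06 = 27.94%, and could take such a result as pointing to a rate below 5%. If the true chance is much higher, the result says little against a 5% rate. The ring is also the product for which protocol section 13.4.1 says no prospective data exist in breastfeeding infants.

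**Working it through.** **Inputs.** Arm sizes n=150 and n=50 (Table 19 footnote). Thresholds 0, 1, 10 and 50 (section 10.5). True rates p of 1, 5, 10, 15 and 25% (Table 19). Each participant counts once (protocol section 10.8.2), so the number of participants with an event, X, is binomial(n, p), assuming independence and a common rate.

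**Formula.** P(X ≥ k) = 1 − Σ C(n, j) pʲ (1 − p)ⁿ⁻ʲ, summed over j = 0 to k − 1.

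**Step 1: columns that reproduce.** At p = 5%, P(0) = 0.95¹⁵⁰ = 0.05% and 0.95⁵⁰ = 7.69%, as printed. All 20 cells for P(0) and P(≥1) match to two decimals. All 26 intervals in Table 20 match exact Clopper-Pearson limits.

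**Step 2: P(≥10), in %.**

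| True rate | Ring printed | Ring exact | Difference | Truvada printed | Truvada exact | Difference |
|---|---|---|---|---|---|---|
| 1% | 8.94 | 0.00 | +8.94 | 0.00 | 0.00 | 0.00 |
| 5% | 72.06 | 21.91 | +50.15 | 0.00 | 0.02 | −0.02 |
| 10% | 96.62 | 94.00 | +2.62 | 0.94 | 2.45 | −1.51 |
| 15% | 99.71 | 99.95 | −0.24 | 11.99 | 20.89 | −8.90 |
| 25% | 99.99 | 100.00 | −0.01 | 73.78 | 83.63 | −9.85 |

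The ring value at 1% is 0.0003% before rounding.

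**Step 3: P(≥50).** For n=150 at 25%, the exact value is 1.36% and the printed one 0.85%, a difference of −0.51 points. The other nine cells are 0.00, as printed.

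**Step 4: other readings of the ring column at n=150.** A strict inequality, the point probability at ten, the lower tail, a Poisson approximation, and a normal approximation with or without continuity correction all fail. At 5%, for example, they give 13.22% for more than ten, 8.69% for exactly ten, 86.78% for ten or fewer, 22.36% for Poisson, and 17.45% or 22.68% for the normal. None is near 72.06%.

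**Step 5: what the printed values match.** A search over sample sizes and thresholds gives a likely source for each.

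- Ring, P(≥10): matches P(X ≥ 2) with n=50. At 5%: 1 − 0.95⁵⁰ − 50 × 0.05 × 0.95⁴⁹ = 1 − 0.0769 − 0.2025 = 0.7206. At 1%, 10% and 15% the same expression gives 8.94, 96.62 and 99.71. At 25% it gives 99.999, which agrees with the printed 99.99 only if truncated.
- Truvada, P(≥10): matches P(X > 10) with n=50, that is 0.94, 11.99 and 73.78 at 10, 15 and 25%. At 15% the gap of 20.89 − 11.99 = 8.90 is exactly P(X = 10).
- Ring, P(≥50) at 25%: matches P(X > 50) with n=150, that is 0.85.

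**Step 6: effect on interpretation.** At a true 5% rate in the ring arm, the chance of fewer than ten events is 100 − 21.91 = 78.09%, against the 27.94% implied by the table.

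**The case against.** The error itself cannot be defended; its importance can be disputed. SAP section 2.5 says that the sample size rests on feasibility, expected low drug concentrations and a likely favourable safety profile, so the tables describe a size already chosen. The figures that the SAP repeats (0.05%, 7.69%, 2.43% and 7.11%) are all correct, and it reaches the wrong columns only through a general reference. No stopping rule, interim analysis or planned test uses the ten-or-more or fifty-or-more probabilities. The primary safety results are proportions with exact intervals. Table 20, on the same page and correct, already guards against the misreading: 8 events in 150 gives 2.33% to 10.24%, which includes 5%. SAP section 2.5 also records that 197 pairs were enrolled, so a correction cannot alter the design.

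All of that stands, and it limits the consequences. So do two points on scope: the fifty-or-more error is one cell and half a point, and only five of the ten wrong cells miss by more than 2 points (ring at 1, 5 and 10%; Truvada at 15 and 25%). The explanation of how the values arose is an inference from matching numbers, since the documents do not say. None of it makes the printed figures correct. Damage in reading the PDF is not a plausible cause, because the neighbouring columns in the same rows reproduce exactly.

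**Conclusion.** The concern holds. Under the binomial model that the protocol's own definitions imply, both ten-or-more columns of Table 19 are wrong. In the ring arm the table overstates the chance of ten or more events at true rates of 1 to 10%, by as much as 50.15 points at 5%. In the Truvada arm it understates that chance by 8.90 and 9.85 points at 15% and 25%. The fifty-or-more error is real but small. The sample size, the planned analyses, Table 20 and the figures quoted in the SAP are unaffected. What needs correcting is the protocol's account of what the design can show on its primary safety endpoints, which section 10.5 also extends to drug detection. The size of the error rests only on the stated arm sizes of 150 and 50, the printed thresholds, and independent participants counted once each.

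**What to change.** Replace these entries in Table 19, for true rates of 1, 5, 10, 15 and 25%:

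- P(≥10), n=150: 0.00, 21.91, 94.00, 99.95, 100.00.
- P(≥10), n=50: 0.00, 0.02, 2.45, 20.89, 83.63.
- P(≥50), n=150, at 25% only: 1.36.

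Issue this as a protocol correction or an erratum, and have SAP section 2.5 cite the corrected table. Relabelling the existing columns would not be a good alternative, since the ring column appears to describe two or more events in 50 participants, which is not a property of that arm. The cost is a table correction and a one-line SAP note. Sample size, data collection and analysis stay the same. The ring arm's stated probabilities at 1, 5 and 10% become less favourable.

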10.6 Participant Accrual, Follow-up and Retention

Time to complete accrual will be approximately 4 - 6 months (16 - 26 weeks). Each enrolled mother-infant pair will be followed for approximately three and a half months (14 weeks). If a mother seroconverts while on study, the infant will have an additional visit, 12 weeks after seroconversion is diagnosed, for additional HIV testing.

10.7 Randomization

Participants will be randomized in a 3:1 ratio (VR:tablet) to the two arms of the study stratified by study site. The randomization scheme will be generated and maintained by the MTN SDMC.

10.8 Data and Safety Monitoring Procedures

No DSMB oversight is planned for this study. The MTN-043 Management Team will review study progress, including rates of participant accrual, retention, completion of primary and secondary endpoint assessments, and study or laboratory issues on monthly calls and make recommendations to resolve any issues identified during those reviews. Safety monitoring will be done by the PSRT.

10.8.1 Statistical Analyses

When the use of descriptive statistics to assess group characteristics or differences is required, the following methods will be used: for categorical variables, the number and percent in each category; for continuous variables, the mean, median, standard deviation, quartiles and range (minimum, maximum). To assess the adequacy of the randomization, participants in each of the two arms will be compared for baseline characteristics including demographics and laboratory measurements using descriptive statistics. No formal statistical comparisons will be performed.

10.8.2 Primary Analyses

An intent to treat analysis will be performed to summarize the frequency of primary endpoints (maternal safety, infant safety and drug detection) by study arm. A secondary analysis will be conducted including only visits in which a participant has been exposed to the study product. Consistent with the primary objectives to describe the safety profile and drug detection in each arm, the number and the percentages of participants experiencing each primary endpoint (see [Section 10.2](#)) will be tabulated by study arm. Each participant will contribute once in each category (i.e., only for highest severity AE for each participant) for the calculation of event rates. Exact binomial confidence intervals will be calculated for each primary endpoint. A secondary analysis will be performed to summarize the total number of primary and secondary safety endpoints reported per participant by study arm.

10.8.3 Analysis of Secondary Endpoints

Adherence: For women randomized to the VR arm, a combination of measures (maternal plasma DPV concentration and residual DPV levels in returned rings) will be used to characterize use of study product. For women randomized to Truvada, maternal plasma concentrations of drug will be used to quantify study product use. The number and proportion of participants visits with concentrations indicative of consistent study product use will be compared by study arm using generalized estimating equations (GEE) with a Poisson link and offset of number of tests for drug concentration. Trends over time in study product use will be explored using generalized estimating equations (GEE). Reasons for study product non-use (i.e. ring removal, missed pills) will be tabulated by arm.

Acceptability: To assess acceptability of the study products, information about acceptability will be obtained from questionnaires in which the participants will rate acceptability on a combination of categorical and continuous scales. Continuous measures of acceptability will be compared across arms using a t-test while categorical measures will be compared using chi-squared tests or Fisher's exact test, as appropriate. The number and percentages of participants who report the study product to be at least as acceptable as other HIV prevention methods will be summarized by study arm. These binomial proportions will be used to assess the acceptability of the study products along with the corresponding 95% confidence intervals and will be compared using chi-squared tests or Fisher's exact test, as appropriate.

10.8.4 Missing Data

We expect little to no missing data. Data will be considered missing (no data on outcome measures) if a participant does not return for a follow-up visit. However, if the probability of missing measurements depends on either covariates or on the measurement outcomes of participants, then the methods described above may give biased inferences and point estimates. If a substantial amount of endpoint data is missing (e.g., follow-up data missing in at least 10% of participants), then secondary analyses of the endpoints will be conducted using methods that relax the missing completely at random assumption to a missing at random assumption. For a univariate binary and quantitative outcome, respectively, a generalized linear model with a binomial or Normal error distribution will be used for estimation and testing. Sensitivity analyses will be conducted comparing the regimens using only the first study product use period data for all the outcomes.

11 DATA HANDLING AND RECORDKEEPING

11.1 Data Management Responsibilities

Study CRFs will be developed by the MTN SDMC in conjunction with the protocol team. Quality control reports and queries routinely will be generated and distributed by the SDMC to the study sites for verification and resolution. As part of the study activation process, each study site must identify all CRFs to be used as source documents. Study data is entered into the electronic CRFs in the MTN-043 Medidata Rave study database, a data management system compliant with *International Council on Harmonization (ICH) Good Clinical Practices (GCP)* and *CFR Guidelines*, which is maintained by the MTN SDMC.

Interview files generated in the field will be electronically transferred to Research Triangle Institute (RTI) International using a secure File Transfer Protocol (FTP) site, where they will be uploaded and managed using a qualitative software package. RTI International will act as a hub and manage all qualitative data for the study. A convention for file naming will be developed, and all data will be labeled according to this process. Transcripts will be transferred to RTI International as they are completed. RTI International will save all versions of all files on a secure, password-protected server.

